2 STUDY OBJECTIVES

2.1 Primary Objective

The primary objective is to assess the efficacy and safety of SPN-810 in reducing the frequency of IA behaviors in pediatric patients with ADHD when taken in conjunction with standard ADHD treatment.

This document is confidential. It contains proprietary information of Supernus® Pharmaceuticals, Inc. Any viewing or disclosure of such information that is not authorized in writing by the Sponsor is strictly prohibited. Such information may be used solely for the purpose of reviewing or performing this study.

2.2 Secondary Objectives

The secondary objectives of the study are to assess the following:

- the effect of SPN-810 on the Clinical Global Impression – Improvement Scale (CGI-I)
- the effect of SPN-810 on the Clinical Global Impression – Severity Scale (CGI-S)
- the effect of SPN-810 on the child's overall health as measured by the Child Health Questionnaire Parent Form 28-item (CHQ-PF28)
- the effect of treating the child with SPN-810 on the parent-child relationship as measured by the Parenting Stress Index – Short Form version 4 (PSI-4-SF)
- the effect of SPN-810 on the caregiver-completed CGI-I
- the effect of SPN-810 on inattention and hyperactivity-impulsivity measured by the SNAP-IV Rating Scale

2.3 Tertiary Objective

3 INVESTIGATIONAL PLAN

3.1 Rationale for Study Design, Including Choice of Treatment Groups, Appropriateness of Measurements

The present study is designed to evaluate the efficacy, safety, and tolerability of SPN-810 in patients aged 6 to 12 years with ADHD and comorbid IA, when taken in conjunction with a standard ADHD treatment. In this patient population, IA behaviors persist, despite monotherapy treatment with an FDA-approved ADHD medication, stimulant or non-stimulant, at an FDA-approved optimized dose.

A titration schedule will be followed to ensure a safe escalation to each dose level. The titration rate and dose range under investigation in the present study were demonstrated to be safe, efficacious, and well tolerated in a similar patient population in the previous Phase 2b study. Administration of study medication will be recorded using an electronic dosing diary.

The IA diary will serve as the primary assessment tool for efficacy. The IA diary is a new electronic observer-reported outcome (eObsRO) instrument developed by the Sponsor to record behaviors associated with IA. Secondary measures of efficacy will include the effect of SPN-810 on the Clinical Global Impression – Improvement Scale (CGI-I), the effect of SPN-810 on the Clinical Global Impression – Severity Scale (CGI-S), the effect of SPN-810 on the child's overall health as measured by the Child Health Questionnaire Parent Form 28-item (CHQ-PF28), and the effect of treating the child with SPN-810 on the parent-child relationship as measured by the Parenting Stress Index – Short Form (PSI-4-SF). The child's ADHD symptoms will be measured using the Swanson, Nolan and Pelham Rating Scale - Revised (SNAP-IV).

Safety will be assessed by the monitoring of AEs, concomitant medications, vital signs, clinical laboratory tests, physical examinations, and ECGs, as well as by the Simpson-Angus Scale, the Barnes Akathisia Scale, and the Abnormal Involuntary Movement Scale (AIMS). The scales were chosen to specifically monitor EPS, since youth treated with antipsychotics are at greater risk for EPS side effects than adults (Findling 2005). These scales were utilized in Phase 2 studies and have been used in other clinical studies of atypical antipsychotics in children.

3.2 Overall Study Design and Plan

Protocol 810P301 is a randomized, placebo-controlled, double blind, multicenter, parallel group, fixed dose study to demonstrate the efficacy, safety, and tolerability of SPN-810 in the treatment of IA in patients aged 6-12 years with ADHD in conjunction with standard ADHD treatment. The study is presented schematically in [Figure 1](#) and [Figure 2](#). The study is divided into three phases: Pre-Treatment, Treatment, and Conversion/Taper.

Following screening, eligible subjects will enter a flexible baseline period, at which time the IA diary will be issued to the subject's primary caregiver. At the end of the baseline period, eligible subjects whose primary caregiver has maintained at least 80% compliance with the IA diary will be randomized 1:1:1 to 18 mg/day SPN-810, 36 mg/day SPN-810, or placebo. A dose titration schedule will be followed, with dosing in the active treatment groups initiated at 3 mg/day and increased approximately every 3 days until the target dose is reached. After completing the two-week titration period and the three-week maintenance period, subjects will enter the conversion or tapering phase prior to discontinuing SM, at which time subjects will have the option to enter an open label extension (OLE) study. A subject who discontinues during the maintenance period prior to Visit 6 may be allowed to participate in the OLE on a case-by-case basis only after consultation between the Investigator, the Medical Monitor and the Sponsor. The OLE study will be conducted under a separate protocol. Subjects who choose to participate in the OLE will enter that study at a dose of 18 mg/day SPN-810.

3.2.1 Pre-Treatment Phase

3.2.1.1 Screening Period

Screening will take place for up to 45 days prior to randomization and may be carried out over more than one visit if necessary. Prior to conducting any screening procedures, written informed consent/assent must be obtained from the parent or legal representative, and subject (when required). Each screened subject will be assigned a subject number starting from 1001 to 1999 in a sequential manner. Staff at study sites are encouraged to complete screening procedures as early as possible to provide more flexibility in the baseline period for the caregivers to achieve IA diary compliance (see [Section 3.2.1.2](#)).

The R-MOAS and CGI-S will be administered to determine entry to the baseline period of the study and also to determine eligibility for randomization to treatment. The Vitiello Aggression Scale will be used to evaluate subtype of aggression (planned vs. impulsive); only those children who score as predominantly

impulsive will be included. The diagnosis of ADHD will be confirmed with the Schedule for Affective Disorders and Schizophrenia for School-aged Children—Present and Lifetime Versions 2013 (K-SADS-PL 2013). The K-SADS-PL 2013 is a semi-structured diagnostic interview designed to diagnose current and past episodes of psychopathology in children and adolescents according to DSM-5 criteria. The Introductory and Screen Interviews will be completed. The Screen Interview will assess the different diagnoses and determine which supplements should be completed. Supplement 4 (Neurodevelopment, Disruptive and Conduct Disorders) must be completed to assess ADHD, ODD, CD, Tic and ASD (Autism Spectrum Disorder). If an exclusionary diagnosis is confirmed, the remainder of the diagnostic will not be completed and the subject will be deemed a screen failure.

3.2.1.2 Baseline Period

Subjects who meet study entry requirements will proceed to the flexible baseline period. At Visit 2 an IA diary device (LogPad) will be issued to the primary caregiver. The primary and (if assigned) secondary caregivers will receive training on the use of the IA diary. Every effort will be made to provide adequate caregiver training on the use of the IA diary at Visit 2 and acknowledgement of training will be captured on the device.

Following at least 15 days of IA diary use, caregiver compliance with the IA diary will be assessed. Compliance will be calculated as the percentage of days over the past 15 days during the baseline period for which an evening diary was completed. Subjects whose caregivers demonstrate at least 80% compliance will be eligible for randomization and continue into the titration period.

Subjects whose caregivers do not reach 80% compliance during the first 15 days of the baseline period may be allowed to continue to use the diary for up to 15 additional days. For these subjects, caregivers will receive remedial training on the use of the IA diary. During this time, caregiver compliance with the IA diary will be monitored daily by study site personnel over the past 15-days as a “rolling window”. When the caregivers’ performance with the IA diary improves such that the caregivers are able to demonstrate at least 80% compliance over the past 15-day rolling window, the subject will be eligible for randomization and allowed to continue into the titration period.

Although there are up to 30 days available for each of the screening and the baseline period, the total duration of screening and baseline periods may not exceed 45 days.

Rescreening

As a general rule, rescreening of subjects is not allowed. The only exception to this will be for subjects who failed screening due to caregiver non-compliance with the IA diary under protocol version 5.0. These subjects may be rescreened to participate in the study under current protocol. These subjects will be assigned a new subject ID number and will complete all study screening procedures.

3.2.2 Treatment Phase

3.2.2.1 *Randomization*

Inclusion/exclusion criteria will be re-assessed to verify eligibility prior to study randomization at the end of Visit 3 (Randomization). Eligible subjects whose primary caregiver has maintained at least 80% compliance with the IA diary will be randomized. Eligible subjects who complete the baseline period and meet the requirements for the double blind study will be randomized at Visit 3 (Day 1) in a 1:1:1 ratio to receive 18 mg/day, 36 mg/day SPN-810, or placebo and proceed to the titration period, which will be two weeks.

3.2.2.2 *Titration Period*

Subjects will be titrated to maintenance dose over a period of 2 weeks.

3.2.2.3 *Maintenance Period*

Following dose titration, subjects on active treatment will be maintained at their designated dose level for 3 weeks.

3.2.3 Conversion/Taper Phase

All subjects who complete the randomized, double blind portion of study 810P301 will have the option to participate in an OLE study (study protocol 810P304) in which all subjects will receive active SM treatment. Subjects choosing to participate will receive blinded conversion medication kits, and their total daily dose for the open label extension will be converted to 18 mg/day ([Figure 1](#)). Those subjects who do not elect to participate in this extension will be tapered off SM ([Figure 2](#)).

3.2.4 End of Study / Early Termination

Subjects will return to the study site for a final visit, after completing the 1-week Taper/Conversion Period. Those subjects who elect to continue in the OLE study will have procedures performed for that study as well. Subjects who discontinue from the study during the maintenance period will be offered a Taper kit and will return to the study site for a follow-up visit (EOS). Subjects who discontinue during the titration period will not receive a taper kit and will only complete the EOS procedures.

Figure 1: Treatment Schedule (Conversion)

[figure not shown]
[figure not shown]

Figure 2: Treatment Schedule (Taper)

4 STUDY METHODS

4.1 Selection of Study Population

The target population will be male and female subjects aged 6 to 12 years with IA and ADHD. SM will be administered in conjunction with the subject's standard ADHD treatment. Approximately 330 subjects will be randomized in this clinical investigation.

4.1.1 Inclusion Criteria

1. Healthy male or female subjects, age 6 to 12 years at the time of screening.
2. Diagnosis of ADHD according to the Diagnostic and Statistical Manual of Mental Disorders- 5 (DSM-5 confirmed by the Schedule for Affective Disorders and Schizophrenia for School-aged Children – Present and Lifetime Version 2013 (K-SADS-PL 2013)).
3. Retrospective Modified Overt Aggression Scale (R-MOAS) score of ≥ 24 at screening.
4. CGI-S score of at least moderately ill at both Screening and Randomization.
5. Vitiello Aggression Scale score from -2 to -5 at Screening.
6. Free of antipsychotic medication for at least two weeks prior to Visit 2.
7. Monotherapy treatment with FDA-approved optimized ADHD medication (psychostimulant or non-stimulant) at an FDA-approved dose for at least one month prior to Screening, and willing to maintain that dose throughout the Baseline and Treatment period.
8. α 2- adrenergic agonists (e.g. clonidine and guanfacine) used for any other reason except for monotherapy treatment for ADHD (e.g. aggression or insomnia) must be discontinued at least two-weeks prior to Visit 2.
9. Medically healthy and with clinically normal laboratory profiles, vital signs, and electrocardiograms (ECGs).
10. Weight of at least 20 kg.
11. Able and willing to swallow tablets whole and not chewed, cut or crushed.
12. Written Informed Consent obtained from the subject's parent or legal representative, and written Informed Assent obtained from the subject if appropriate.
13. Measurement of compliance $\geq 80\%$ for completion of IA Diary during Baseline Period.

4.1.2 Exclusion Criteria

1. Body Mass Index (BMI) in 99th percentile or above.
2. Current or lifetime diagnosis of epilepsy, major depressive disorder, bipolar disorder, schizophrenia or related disorder, personality disorder, Tourette's disorder, or psychosis not otherwise specified.
3. Currently meeting DSM-5 criteria for autism spectrum disorder, pervasive developmental disorder, obsessive compulsive disorder, post-traumatic stress disorder, or any other anxiety disorder as primary diagnosis.

4. Use of anticonvulsants including carbamazepine and valproic acid, antidepressants, mood stabilizers including lithium, benzodiazepines, cholinesterase inhibitors or any drug known to inhibit CYP2D6 activity within two weeks of Visit 2.
5. Use of herbal supplements within one week of Visit 2.
6. Known or suspected intelligence quotient (IQ) < 70.
7. Unstable endocrinological or neurological conditions which confound the diagnosis or are a contraindication to treatment with antipsychotics.
8. Suicidality, defined as either active suicidal plan/intent or active suicidal thoughts in the six months before the Screening Visit or more than one lifetime suicide attempt.
9. Pregnancy or refusal to practice contraception during the study (for female subjects of childbearing potential and sexually active males).
10. Substance or alcohol use during the last three months.
11. Urine drug test at screening that is positive for alcohol or drugs of abuse.
12. Known allergy or sensitivity to molindone hydrochloride.
13. Any reason which, in the opinion of the Investigator or the Sponsor, would prevent the subject and subject's caregiver from participating in the study or complying with the study procedures.
14. Use of an investigational drug or participation in an investigational study within 30 days prior to Visit 2.

4.2 Schedule of Visits and Procedures

All subjects who are randomized and take any SM will be followed according to the protocol regardless of the number of doses of SM taken, unless consent for follow-up is withdrawn. The Sponsor, or the Sponsor's designee, must be notified of all deviations from the protocol visits or procedures, and these procedures, if applicable, will be rescheduled or performed at the nearest possible time to the original schedule. Subjects will be instructed to call study personnel to report any abnormalities during the intervals in between study visits and to come to the study site if medical evaluation is needed and as the urgency of the situation indicates. Unscheduled visits may be conducted at the discretion of the investigator throughout all study periods. The medical monitor must be contacted promptly in the event that any clinically significant findings or information are obtained during the unscheduled visit. This should be captured in the appropriate eCRF. For emergency and other unscheduled visits to a medical facility other than the study site, medical records will be obtained by the Investigator or qualified designee as source data for study follow-up.

[Table 1](#) presents the schedule of visits and procedures for the study.

Table 1: Schedule of Visits and Procedures

Phase	Pre-treatment		Treatment				Conversion/ Taper
	Screening	Baseline	Titration		Maintenance		
Period	1	2	3	4	5	6	7
VISIT NUMBER	1	2	3	4	5	6	7
DAY	-45	-15	1	8	15	36	43
WINDOW (DAYS)	≤45d prior to Visit 3	≥15d prior to Visit 3	0 ^c	7d±2d from Visit 3	14d±2d from Visit 3	21d±3d from Visit 5	7d±1d from Visit 6
Informed Consent/Assent ^a	X ^b						
R-MOAS, K-SADS-PL 2013 & Vitiello Aggression Scale	X						
Medical History	X		X ^d				
Demographics	X						
Physical Examination	X					X	
ECG (12-lead)	X			X		X	
Inclusion/Exclusion Criteria	X						
Randomization			X ^{b,e}				
Urine Drug Screen	X		X				
Urine Pregnancy Test ^f	X		X				X
Diary Training & Distribution or Evaluation		X	X ^e	X	X	X	
Vital Signs ^g	X						X
Weight, height, BMI	X		X	X	X	X	X
Hematology/chemistry/Urinalysis	X		X			X	X
PK Blood Sampling				X ^h	X ^h		
Columbia Suicide Severity Rating Scale (CSSRS)	X		X	X	X	X	X
Investigator CGI-S	X		X	X	X	X	
Caregiver and investigator CGI-I				X	X	X	
Efficacy scales (SNAP-IV, CHQ-PF28, PSI-4-SF)			X			X	
Safety Scales (Simpson-Angus, Barnes, AIMS)			X	X	X	X	X
Infrequent Behaviors Checklist			X	X	X	X	
Adverse Events			X	X	X	X	X
Concomitant Medications	X	X	X	X	X	X	X
Drug Dispensation			X ^b		X	X	

Phase	Pre-treatment		Treatment				Conversion/ Taper
Period	Screening	Baseline	Titration		Maintenance		
VISIT NUMBER	1	2	3	4	5	6	7
DAY	-45	-15	1	8	15	36	43
WINDOW (DAYS)	≤45d prior to Visit 3	≥15d prior to Visit 3	0 ^c	7d±2d from Visit 3	14d±2d from Visit 3	21d±3d from Visit 5	7d±1d from Visit 6
Drug Return and Compliance					X	X	X
Diary Return							X

a Written consent must be obtained prior to performing any study-related procedure.
 b Access IWRS.
 c Visit 3 will occur at least 15 days following Visit 2.
 d Assess for any clinically significant change in Medical History since screening.
 e Diary compliance must be at least 80% (minimum of 12 days out of 15) to qualify for randomization.
 f To be performed for female subjects of childbearing potential prior to administration of first dose of SM and will have to be tested as negative for the subject to continue in the study.
 g Heart Rate (HR), blood pressure (BP), temperature, and respiratory rate will be measured.
 h Total of 5 PK blood samples will be obtained over one or two visits (Visit 4 and/or Visit 5)

4.2.1 Visit 1

Prior to conducting any screening procedures, written Informed Consent must be obtained from the parent or legal representative, and, if appropriate, Informed Assent from the subject. Subject screening procedures will be performed within 45 days prior to Visit 3 and may be done on more than one day. Abnormal results on screening laboratory tests may be repeated at the discretion of the Investigator.

The following procedures will be performed at Visit 1:

1. Obtain written informed consent and assent.
2. Obtain demographic information, medical history
3. Access Interactive Web Response System (IWRS) for subject number
4. Administer K-SADS-PL 2013 for confirmation of ADHD diagnosis
5. Administer Vitiello Aggression Scale
6. Administer R-MOAS
7. Administer Investigator CGI-S
8. Perform physical examination
9. Record vital signs (HR, BP, temperature, and RR), height, weight and BMI
10. Perform 12-lead ECG
11. Collect blood samples for hematology and chemistry
12. Administer C-SSRS
13. Collect urine sample for urinalysis and urine drug screen (all subjects), and pregnancy test (FOCBP only)
14. Assess and record concomitant medications
15. Assess inclusion/exclusion criteria

4.2.2 Visit 2

Visit 2 will occur at least 15 days prior to Visit 3. Please note that, per protocol and within the EDC, Visit 1 and Visit 2 may occur on the same day.

1. Provide training for IA diary and dosing diary module
2. Distribute device
3. Assess and record concomitant medications

4.2.3 Visit 3

Visit 3 will occur at least 15 days following Visit 2 according to the Schedule of Visits and Procedures.

1. Administer efficacy scales (SNAP-IV, CHQ-PF28, PSI-4-SF)
2. Assess IA diary compliance / review training as necessary
3. Confirm eligibility to randomize to study medication treatment
4. Randomize subject via IWRS
5. Administer Investigator CGI-S
6. Administer Infrequent Behaviors Checklist

7. Administer safety scales (Simpson-Angus, Barnes Akathisia, AIMS)
8. Record height, weight, and BMI
9. Collect blood samples for hematology/chemistry
10. Collect urine samples for urinalysis, urine drug screen (all subjects), and pregnancy test (FOCBP only)
11. Administer C-SSRS
12. Record concomitant medication
13. Assess for any clinically significant change in Medical History
14. Dispense SM via IWRS.
15. Review training on dosing diary module
16. Assess adverse events (post-dose)

4.2.4 Visit 4

Visit 4 will occur 7 (± 2) days following Visit 3 according to the Schedule of Visits and Procedures.

1. Administer Investigator CGI-S
2. Administer caregiver and investigator-completed CGI-I
3. Administer Infrequent Behaviors Checklist
4. Administer safety scales (Simpson-Angus, Barnes Akathisia, AIMS)
5. Record height, weight, and BMI
6. Perform 12-lead ECG
7. Collect blood samples for PK analysis
8. Administer C-SSRS
9. Record concomitant medication
10. Review IA diary compliance and provide training as required
11. Collect AEs
12. Review dosing diary compliance and provide training as required

4.2.5 Visit 5

Visit 5 will occur 14 (± 2) days following Visit 3 according to the Schedule of Visits and Procedures.

1. Administer Investigator CGI-S
2. Administer caregiver and investigator-completed CGI-I
3. Administer Infrequent Behaviors Checklist
4. Administer safety scales (Simpson-Angus, Barnes Akathisia, AIMS)
5. Record height, weight, and BMI
6. Collect blood samples for PK analysis
7. Administer C-SSRS
8. Record concomitant medication
9. Review IA diary compliance and provide training as required
10. Collect AEs
11. Collect returned SM; assess treatment compliance
12. Review dosing diary compliance and provide training as required

13. Dispense SM

4.2.6 Visit 6

Visit 6 will occur 21 (± 3) days following Visit 5 according to the Schedule of Visits and Procedures.

1. Administer efficacy scales (Investigator CGI-S, caregiver and investigator CGI-I, SNAP-IV, CHQ-PF28, PSI-4-SF)
2. Administer Infrequent Behaviors Checklist
3. Administer safety scales (Simpson-Angus, Barnes Akathisia, AIMS)
4. Record height, weight, and BMI
5. Perform 12-lead ECG
6. Perform physical examination
7. Collect blood samples for hematology/chemistry
8. Collect urine sample for urinalysis
9. Administer C-SSRS
10. Record concomitant medication
11. Review IA diary compliance and provide training as required
12. Collect AEs
13. Collect returned SM; assess treatment compliance
14. Review dosing diary compliance and provide training as required
15. Determine whether subject wishes to participate in open-label extension
16. Dispense SM (either Conversion or Taper based upon subject's decision about participation in open-label extension)

4.2.7 Visit 7

Visit 7 will occur 7 (± 1) days following Visit 6 according to the Schedule of Visits and Procedures. These procedures will also be performed for patients who discontinue early. Patients who discontinue early after Visit 5 will be offered a taper kit.

1. Administer safety scales (Simpson-Angus, Barnes Akathisia, AIMS)
2. Record vital signs (HR, BP, temperature, and RR), height, weight and BMI
3. Collect urine sample for pregnancy test (FOCBP only)
4. Administer C-SSRS
5. Record concomitant medication
6. Collect AEs
7. Collect SM and assess treatment compliance
8. Collect device
9. Complete/discontinue subject
10. Collect blood samples for hematology/chemistry
11. Collect urine sample for urinalysis

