4.6 Completion of Study and Discontinuation of Subjects

Subjects will be considered to have completed the study if they complete all visits up to and including Visit 6. All subjects who discontinue early will complete Visit 7. Any subject who discontinues from the study after Visit 5 will be offered a Taper kit.

The Investigator(s) or subjects themselves may stop SM treatment at any time for safety or personal reasons. A subject is free to withdraw from the study at any time for any reason without prejudice to their future medical care by the physician or at the institution. The Investigator or Sponsor may also withdraw the subject at any time in the interest of subject safety. The withdrawal of a subject from the study should be discussed where possible with the Medical Monitor and/or CRA before the subject stops SM. Subjects removed from the study for any reason will not be replaced.

Reasons for withdrawal may include but are not limited to subject withdrawal of consent, occurrence of unmanageable AEs, or if it is in the best interest of the subject as per Investigator's discretion.

The primary reason for withdrawal must be recorded in the subject's medical record and on the eCRF. If a subject is withdrawn for more than one reason, each reason should be documented in the source document and the most medically significant reason should be entered on the eCRF.

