5.2.4 Parenting Stress Index-Short Form (PSI-4-SF)

Reduction in stress is considered important for parents of children with disruptive behavior problems, developmental disabilities, and chronic illness (Haskett 2006). The Parenting Stress Index – Short Form (PSI-4-SF) is a 36-item self-report measure of parenting stress (Abidin 1995). Three subscales (Parental Distress, Parent-Child Dysfunctional Interaction, and Difficult Child) consist of 12 items each. Parents use a 5-point scale to indicate the degree to which they agree with each statement.

The PSI-4-SF will be administered at Visit 3 and Visit 6.

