6.9.2 Secondary Efficacy Analyses

The secondary endpoints are:

1. Actual Caregiver CGI-I score at Visit 6
2. Actual Investigator CGI-I score at Visit 6
3. Change from Visit 3 to Visit 6 in Investigator CGI-S score
4. Change from Visit 3 to Visit 6 in CHQ-28 score
5. Change from Visit 3 to Visit 6 in PSI-4-SF scores in:
 - a. Parental Distress
 - b. Parent-Child Dysfunctional Interaction
 - c. Difficult Child
6. Change from Visit 3 to Visit 6 in SNAP-IV ADHD scores in:
 - a. Inattention ratings
 - b. Hyperactivity/Impulsivity ratings
 - c. Combined Scale ratings

Each one of the six secondary endpoints will be analyzed using the analysis of covariance method based on the ITT population with missing data imputed using the Last Observation Carried Forward (LOCF) method. The model includes treatment and baseline as fixed independent covariates and change from baseline to final maintenance visit as a response variable. The least squares mean of each treatment group, the difference in the least squares mean (18mg dose minus placebo and 36 mg dose minus placebo), and the 2-sided 95% CI for the difference will be obtained.

To preserve the overall type I error rate at 0.05 for the secondary endpoints, a sequential testing procedure will be used with the following features. First only dose or doses that are significantly different from placebo for the primary endpoint will be tested for secondary endpoints. The first of the secondary endpoints will be compared to placebo using the Hochberg step up procedure but only using those doses retained as a result of testing the primary endpoint (Hochberg 1988). The second secondary endpoint will be tested in the same manner but only using those doses that were retained from the

primary and the first secondary endpoint and so forth. As the endpoints are gone through in the pre-defined order doses will only be retained if significant for all endpoints tested so far and at the given stage the Hochberg step-up procedure will be applied.

The ordering of the 6 secondary endpoints from first to be tested to sixth is: Investigator Clinical Global Impression – Improvement Scale (CGI-I)(Endpoint 1), Clinical Global Impression – Severity Scale (CGI-S) (Endpoint 2), Child Health Questionnaire (CHQ-28) (Endpoint 3), Parenting Stress Index (PSI-4-SF) (Endpoint 4), Caregiver-completed CGI-I (Endpoint 5) and SNAP-IV Rating Scale (Endpoint 6).

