6.2 Visit Window and Unscheduled Assessments

There is no visit window for the by visit analysis. Data will be analyzed according to the visit they are associated with. Data collected at unscheduled time points will not be summarized at the unscheduled time points. However, the unscheduled data will be used for analysis if data are missing at the next scheduled visit due to early termination.

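### Subjects who leave the study before Visit 6 have no scheduled post-baseline SNAP-IV, CHQ-PF28 or PSI-4-SF, so under the SAP three secondary endpoints labelled ITT use only those who reach Visit 6

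*Protocol*

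**What the plan says.** **Collection.** Protocol 5.2.2 to 5.2.4 and Table 1 place SNAP-IV, CHQ-PF28 and PSI-4-SF at two visits only. For the last of these: "The PSI-4-SF will be administered at Visit 3 and Visit 6". SAP 5.2 repeats the schedule. CGI-S and both CGI-I ratings are also taken at Visits 4 and 5 (Protocol 5.2.1).

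**Leavers.** Protocol 4.6 defines completion by Visit 6 ("Subjects will be considered to have completed the study if they complete all visits up to and including Visit 6") and sends everyone else to the last visit: "All subjects who discontinue early will complete Visit 7". Protocol 3.2.4 adds, for leavers in titration: "Subjects who discontinue during the titration period will not receive a taper kit and will only complete the EOS procedures". Protocol 4.2.7 says of the Visit 7 list: "These procedures will also be performed for patients who discontinue early". The eleven Visit 7 items in Protocol 4.2.7 are the movement-disorder scales, vital signs and body size, pregnancy test, C-SSRS, concomitant medication, adverse events, drug return, device return, close-out, blood tests and urinalysis.

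**Analysis.** Protocol 6.9.2 analyses all six secondary endpoints by analysis of covariance "based on the ITT population with missing data imputed using the Last Observation Carried Forward (LOCF) method". The SAP states in its introduction that it supersedes the protocol's methods. SAP 7.7.7 bases all secondary analyses on the ITT population, gives a repeated-measures model (MMRM) for CGI-I and CGI-S only, and analyses the other three scales by ANOVA at Visit 6. SAP 6.4 names MMRM for missing secondary data in general. SAP 6.2 adds that "the unscheduled data will be used for analysis if data are missing at the next scheduled visit due to early termination".

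**The concern.** ITT membership needs one dose, a baseline and one valid post-randomisation diary assessment (SAP 7.1.2). A subject can therefore leave in week 2, belong to the ITT population, and have nothing after Visit 3 on three secondary endpoints. The diary primary endpoint keeps what was recorded up to leaving; these scales keep nothing.

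The three endpoints sit in a testing sequence meant to control type I error. In the protocol's order CHQ-PF28 and PSI-4-SF come third and fourth, ahead of caregiver CGI-I; in the SAP's list the three scales come fourth to sixth. If leaving is related to outcome, the comparison at Visit 6 is selected on outcome. That is plausible here, because titration is forced and dose reduction is not permitted (Protocol 4.3.6). The planned missing-data sensitivity analyses (Protocol 6.9.3, SAP 7.7.2) cover the primary endpoint only.

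**Working it through.** **1. What a leaver can supply** (Protocol Table 1 and 4.2.3 to 4.2.7)

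| Measure | V3 | V4 | V5 | V6 | V7/EOS |
|---|---|---|---|---|---|
| SNAP-IV, CHQ-PF28, PSI-4-SF | yes | no | no | yes | no |
| Investigator CGI-S | yes | yes | yes | yes | no |
| CGI-I, investigator and caregiver | no | yes | yes | yes | no |

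In the first row, anyone who goes from any point before Visit 6 straight to Visit 7 has a baseline and nothing else.

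**2. What each missing-data rule does with that record**

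- ANOVA at Visit 6 (SAP 7.7.7): no Visit 6 value, so the subject drops out of the analysis.
- MMRM (SAP 6.4): not specified for these scales. With Visit 6 as the only post-baseline visit, a leaver would have no response record, so the result would be the same.
- LOCF (Protocol 6.9.2): only the Visit 3 value can be carried, which is a change of zero. The subject is counted, but with an unmeasured outcome. With equal dropout of 20%, the difference in mean change becomes (1 − 0.20) = 0.80 of the difference among completers.
- Unscheduled data (SAP 6.2): usable if they exist, but no document schedules these scales at an early-termination contact.

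**3. The plan's own figures**

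- Protocol 6.10: 264 / (1 − 0.20) = 330 randomised, as stated; 330 / 3 = 110 per arm.
- SAP 3.5: 122 / (1 − 0.20) = 152.5, rounded up to 153 per arm, as stated.

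(The protocol also gives 132 per arm, which does not fit 264 across three arms, since 3 × 132 = 396. That is a separate matter; I use 330 and the 1:1:1 ratio.)

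**4. Number without a Visit 6 value, dropout equal across arms**

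- Protocol: 110 × 0.20 = 22 per arm, or 66 of 330.
- SAP: 153 × 0.20 = 30.6, about 31 per arm, or about 92 of 459.
- If dropout were 10% to 30% (assumed range): 11 to 33 of 110, or about 15 to 46 of 153.

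Leavers with no post-randomisation diary entry are outside the ITT population, so the count within ITT is somewhat lower.

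**5. Possible bias.** Let d be the dropout fraction, C the completer mean and L the leaver mean, in SD units. The full-arm mean is (1 − d)C + dL, so the completer mean is off by d(C − L). The error in the treatment difference is this quantity in the active arm minus the same quantity in placebo. With d = 0.20 and assumed values of C − L:

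- One arm only, 0.25 to 0.5 SD: 0.20 × 0.25 = 0.05 SD, to 0.20 × 0.5 = 0.10 SD.
- Both arms, same size and direction: 0.
- Both arms, opposite directions: 2 × 0.05 = 0.10 SD, to 2 × 0.10 = 0.20 SD.

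The documents give no value for C − L.

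**The case against.** The strongest reply is that the gap is narrower and less consequential than it first looks. Much of it stands.

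- **Stopping drug is not leaving the study.** A reader might infer that everyone who stops treatment before Visit 6 is lost to these scales. Protocol 4.2 and SAP 3.2 follow every treated subject whatever the number of doses taken, unless consent for follow-up is withdrawn. Someone who stops drug but remains can reach Visit 6. The point covers subjects who leave the study.
- **Not every secondary endpoint is affected alike.** CGI has Visits 4 and 5 and an MMRM. What CGI lacks is a rating at the time of leaving.
- **Completer-only is a property of the SAP analysis.** A reader might attach it to the protocol as well, but LOCF would count leavers with zero change.
- **Early values are not barred.** Protocol 4.2 allows unscheduled visits in all periods and SAP 6.2 would use the data. But nothing asks for these scales then, so any such value would exist by chance.
- **Imputation is possible.** Diary and CGI data could inform a model for the missing scales. None is planned, and it would replace an outcome that could have been measured.
- **The consequence is limited.** These endpoints are tested only after the primary and earlier secondary endpoints succeed, and differences between leavers and completers may cancel between arms.

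These points narrow the claim. None supplies a scheduled post-baseline value for a study leaver.

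**Conclusion.** The gap is real and structural. Study leavers before Visit 6 have no scheduled post-baseline SNAP-IV, CHQ-PF28 or PSI-4-SF, and the SAP's Visit 6 ANOVA omits them while calling the analysis ITT. At the sponsor's assumed 20% dropout this is about 22 of 110 to 31 of 153 per arm, depending on which document's sample size applies and assuming equal dropout.

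The bias is not known. The 0.05 to 0.10 SD figure holds only if leavers in one arm differ from completers by 0.25 to 0.5 SD; it could be nil or larger. It would be wrong to conclude that the primary endpoint is compromised. This is an inexpensive improvement to three gated secondary endpoints and worth making.

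**What to change.** **Protocol 4.2.7, 4.6 and Table 1 (and SAP Table 1).** Require subjects who leave the study before Visit 6 to complete SNAP-IV, CHQ-PF28, PSI-4-SF, Investigator CGI-S and both CGI-I ratings at the discontinuation or end-of-study contact, recorded as early-termination values. State there that subjects who stop drug but remain in follow-up keep the ordinary schedule.

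**SAP 6.2, 6.4 and 7.7.7.** State the use of early values scale by scale:

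- SNAP-IV and PSI-4-SF: include them in the Visit 6 ITT analysis, with a Visit-6-only analysis as sensitivity.
- CGI-S and CGI-I: assign them to the next scheduled visit, as SAP 6.2 implies. Placing them all at Visit 6 would bring a form of LOCF into the MMRM, and the SAP replaced LOCF.
- CHQ-PF28: use them in a sensitivity analysis only. Most items ask about the past four weeks. For a subject assessed by Day 15, at most 14 of those 28 days follow the first dose, so the window overlaps baseline.
- Correct SAP 6.4 so that it does not imply an MMRM for the three scales with one post-baseline visit.

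**Cost.** One amendment, and existing questionnaires for up to about one subject in five at a contact they are already asked to attend, with some added caregiver time. Early values reflect shorter exposure, hence the flag. Subjects lost to follow-up or refusing the visit will still supply nothing. Subjects who left before the amendment cannot be recovered, and the SAP's sample size text shows that the interim review has already taken place. Collection would therefore differ between stages, and the number of early values should be reported by arm and stage.
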